# 6.15.2 Replacements

Patients who terminate early from the study will not be replaced.

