	
To be eligible to enroll in the extension study APD811-007, patients must complete study APD811-003. Additionally, placebo treated patients who discontinue study drug treatment due to clinical worsening in APD811-003 will be permitted to enroll in APD811-007, upon approval of the medical monitor, provided that all end of study procedures including right heart catheterization are performed per protocol.
 
Patients will be receiving concomitant oral disease-specific PAH therapy consisting of an endothelin receptor antagonist (ERA) and/or an agent acting on the nitric oxide pathway, a PDE5 inhibitor or a soluble guanylate cyclase stimulator, provided the dose has remained stable for at least 3 months prior to the start of Screening. Patients should continue the same dose and regimen of these medications for the duration of the study.
 
The use of the following therapies, which may affect PAH, are permitted:
 
Vasodilators (including calcium channel blockers), digoxin, spironolactone, or L-Arginine supplementation; if on a stable dose for at least 1 month prior to the start of Screening and should remain unchanged during the study.
 
Doses of spironolactone and digoxin may be held or reduced as necessary to protect the patient’s safety. Doses may not be increased in the month before Day 1 and during the controlled study.
 
Diuretics may be dosed as clinically indicated throughout the study.
 
Intravenous inotropes within 1 month of starting Screening are not permitted.
 
In an attempt to maintain balance across treatment groups, the following stratification factor will be utilized during patient randomization:
 
 • Baseline WHO/NYHA Functional Class (Class II vs III or IV) 
If a patient’s participation in the study is discontinued early, all end of study (EOS) safety and efficacy evaluations are to be performed as part of the Week 22/Early Termination visit. The EOS visit for early terminations will be followed by a follow-up visit to ensure appropriate patient safety at Week 25. If the patient is unable to return for the follow-up visit, AE and concomitant medication follow-up may be conducted by telephone.

Study Site:
	
Multiple centers in United States, Europe, and Australia.

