4.2 Analysis Population

The primary analysis of the efficacy endpoint, PVR, will be conducted using the intent to treat population.

Intent-to-Treat Population (ITT):

This population consists of all patients randomized who receive at least one dose of study drug, and have a baseline PVR measurement. Under this approach, patients are counted in the treatment group to which they were randomized, regardless of the treatment received during the course of the trial. The primary endpoint, PVR change from baseline at Week 22, will use this population for analysis.

Unless otherwise specified, the analyses of all other efficacy variables will use the modified intent to treat (MITT) population as primary. The completers population will be used as a secondary analysis population.

Modified Intent-to-Treat Population (MITT):

This population consists of all patients randomized who received at least one study dose, have a baseline measurement, and have a post-randomization measurement. Under this approach, patients are counted in the treatment group to which they were randomized, regardless of the treatment received during the course of the trial.

Completers Population (CP):

This population consists of all patients who completed the study treatment at Week 22. No missing data will be imputed for this analysis. Any substantial differences between conclusions based on the ITT, MITT and the completers' populations will be investigated.

Safety Population (SP):

The Safety Population will include all randomized patients who received at least one dose of study medication.

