4.3 Approaches to Efficacy Analysis

4.3.1 Primary Efficacy Analysis

The primary efficacy hypothesis regarding the superiority of APD811 to placebo will be assessed in a stepwise manner. First, the statistical significance of APD811 versus placebo result will be determined for the change from baseline in PVR at the end of 22 weeks of treatment. If the result is significant ($p < 0.05$, two-sided), the primary hypothesis will be considered satisfied and this study will be declared positive. Subsequently, the change from baseline in 6MWD will only be formally tested if the change from baseline in PVR is significant. This testing procedure preserves the overall Type I error rate for testing the primary efficacy hypothesis.

In this first-in-patient Phase 2 study in PAH patients, there is a clinical rationale to specify two important primary endpoints: the key hemodynamic parameter, PVR; exercise capacity as measured by 6MWD. Right heart catheterization from which PVR is derived only takes place at Screening and Week 22; 6MWD is measured at Screening, baseline, and at 5 post-baseline specified time points.

In cases of missing data occurring at Week 22, the following missing data handling rules will apply.

For PVR, assessments measured at Week 22 or at time of early withdrawal will be included in the analysis. Missing data at Week 22 will be imputed using the method of multiple imputation as outlined in Section 7.4 and detailed in Appendix 4. For 6MWD, missing values will be imputed with the last observation carried forward (LOCF), except if any patient withdraws early due to death or due to clinical worsening without a 6MWT being measured at a termination visit, a worst value of 0 for 6MWD will be imputed. Baseline assessments will not be carried forward.

To further assess missing data impacts on primary analyses, the completers analyses without data imputation will be performed and compared with additional sensitivity analyses specified in Section 7.4.

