An analysis of covariance (ANCOVA) model with baseline PVR as a covariate and treatment and baseline WHO/NYHA functional class (II vs, III or IV) and baseline background PAH therapy (With ERA vs. Without ERA) as factors will be used to assess the effect of APD811 on change from baseline in PVR. LSM means for the treatments and the treatment effect and LS Mean difference between treatment will be displayed with 95% CIs and the two-sided p-value will be displayed. The normality of the model residuals will be assessed using Shapiro-Wilks test. Assumptions for the analysis of covariance will be checked, and if not satisfied, parametric analyses will be corroborated with appropriate nonparametric analyses, such as the Wilcoxon rank sum test stratified by baseline WHO/NYHA functional class (II vs, III or IV) and baseline background PAH therapy (With ERA vs. Without ERA). The Hodges-Lehmann estimation of location shift and confidence interval will be produced. If the model residuals is not normally distributed, ANCOVA analysis based on log-transformed data will be performed.

Six minute walking distance (6MWD) will be analyzed using the above ANCOVA method described for PVR, substituting the 6MWD baseline measurement as the covariate. Assumptions for the analysis of covariance will be checked, and if not satisfied, parametric analyses will be corroborated with nonparametric analyses, such as the Wilcoxon rank sum test stratified by baseline WHO/NYHA functional class (II vs, III or IV) and baseline background PAH therapy (With ERA vs. Without ERA). The Hodges-Lehmann estimation of location shift and confidence interval will be produced.

Note that formal testing for secondary and exploratory endpoints will proceed only if the comparison for the change from baseline in PVR is significant. In the event that the treatment effect for PVR is non-significant all subsequent testing of other endpoints will be interpreted only in an exploratory, rather than confirmatory manner.

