7 STATISTICAL TECHNICAL ISSUES

7.1 Planned Statistical Power and Sample Size

For the APD811 versus placebo comparison, 28 patients in the APD811 group and 14 patients in the placebo group will have 90% power to detect a between-treatment difference of 350 dyn·s·cm⁻⁵ in PVR. This calculation was based upon the pooled SD estimate of 320.3 dyn·s·cm⁻⁵ for the mean change from baseline in PVR at Week 17 observed in the selexipag phase 2 study.

Assuming that up to 30% of patients may drop out of the trial before a post-randomization repeat RHC is performed, 40 patients will be randomized to the APD811 group and 20 patients will be randomized to the placebo group. For 6MWD, 40 patients in APD811 group and 20 patients in the placebo group will have 80% power to detect a between-treatment difference of 50 meters in 6MWD assuming pooled SD estimate of 65 meters.

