7.4 Handling of Missing Data and Sensitivity Analysis

For the ITT analysis of PVR missing week 22 assessments will be derived using the method of multiple imputation via the SAS/STAT procedure PROC MI and the fully conditional

specification (FCS) method to create 100 imputations resulting in 100 complete datasets. The 100 imputed datasets will then be analyzed using the methods described in Section 4.3.1, with the results of the analyses performed on the 100 datasets combined via PROC MIANALYZE. The imputation model will include the following variables: treatment, baseline PVR, baseline NYHA/WHO functional class category, baseline PAH therapy, baseline values for 6MWD, BNP, NT-proBNP, etiology, last on-treatment 6MWD and whether or not a patient experienced clinical worsening. It is anticipated that the imputation model will converge but should it not do so terms will be removed from the model to achieve convergence. The effects of any such model adjustment will be investigated.

To assess the impact of missing data and robustness of the results, the following sensitivity analyses will be performed for the primary, secondary and selected exploratory endpoints:

- Completers population analyses on primary and secondary efficacy endpoints will be performed without missing data imputation.
- Worst case imputation. For PVR, in all-treated patients, prior to ANCOVA analyses as detailed in Section 4.3.1 missing data at Week 22 due to any reason will be imputed by taking:
 - the worst percentage change from baseline in all patients regardless of treatment group.
 - the baseline observation carried forward.
- An additional 'tipping point analysis' *may* be performed for PVR, post-hoc, in the event that the primary analysis is statistically significant and at least 1 of the worst case imputation analyses yields a non-significant result.

For the proportion of patients who progress to clinical worsening, a sensitivity analysis to assess the impact of missing data will be performed wherein all patients who prematurely discontinue treatment for any reason will be considered to have had a clinical worsening event.

- Imputation of missing or incomplete AE start date
 - If year part of AE start date is missing, then the year of the first treatment date will be assigned.
 - If both month and day part of AE start date are missing, and the year part is the same as year of the first treatment date, then the first treatment date will be assigned;

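### Does the 80% power for 6MWD need restating because it ignores the PVR gate and does not define the 65 m SD?

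*SAP*

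**What the plan says.** SAP 7.1 gives one power figure for the walk test: "For 6MWD, 40 patients in APD811 group and 20 patients in the placebo group will have 80% power to detect a between-treatment difference", with the difference set at 50 m and the pooled SD at 65 m. Protocol 9.3 and both synopses repeat it.

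The sentence follows the PVR calculation: 28 and 14 patients, a difference of 350 dyn·s·cm⁻⁵, an SD of 320.3 for change from baseline, and 90% power. The 28 and 14 are then raised to 40 and 20 to cover up to 30% dropout before the repeat catheterization.

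SAP 4.3.1 sets the order of testing: "the change from baseline in 6MWD will only be formally tested if the change from baseline in PVR is significant". It also fixes the model: "Six minute walking distance (6MWD) will be analyzed using the above ANCOVA method described for PVR, substituting the 6MWD baseline measurement as the covariate".

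Missing data are treated differently for the two endpoints.

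- **PVR** (SAP 7.4): "For the ITT analysis of PVR missing week 22 assessments will be derived using the method of multiple imputation".
- **6MWD** (SAP 4.3.1): the last walk is carried forward, and 0 m is assigned after death or clinical worsening without a termination walk. "Baseline assessments will not be carried forward".

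The MITT population used for 6MWD requires that patients "have a baseline measurement, and have a post-randomization measurement" (SAP 4.2). For patients who stop early, the SAP synopsis says "all end of study (EOS) safety and efficacy evaluations are to be performed as part of the Week 22/Early Termination visit". Protocol 6.15.2 adds: "Patients who terminate early from the study will not be replaced".

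**The concern.** 6MWD is one of two primary hypotheses, and 80% is the only power figure given for it. Three features make that figure look too generous.

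1. **The gate.** A formal 6MWD claim needs PVR to succeed first, and PVR is itself planned at 90%. The chance of passing both cannot exceed the chance of passing 6MWD alone.
2. **Loss of patients.** PVR is powered on 28/14 and inflated for dropout. The next sentence powers 6MWD on the full 40/20 with no margin.
3. **The SD.** The PVR SD has a stated type and source. The 65 m SD has neither, although the analysis adjusts for baseline 6MWD.

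A reader who took 80% as the chance of formally demonstrating a 50 m effect could be over-optimistic about the second primary hypothesis. At stake is how the power statement is read. Type I error and the rule for declaring the study positive are not involved.

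**Working it through.** **Inputs.** From SAP 7.1: 6MWD difference 50 m, SD 65 m, 40/20; PVR difference 350, SD 320.3, 28/14. From SAP 4.3.1: two-sided 0.05. Assumed, because the documents give no value: the correlation between the two test statistics (0 to 0.8), and the correlation of the baseline covariate with the change.

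**Step 1: reproduce the stated figures.** The standard error is SD × √(1/n₁ + 1/n₂), and the noncentrality is the difference divided by the standard error.

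- 6MWD: 65 × √(1/40 + 1/20) = 17.80, and 50/17.80 = 2.81. Power = Φ(2.81 − 1.96) = 80.2%. Noncentral t on 58 df gives 78.9%.
- PVR: 320.3 × √(1/28 + 1/14) = 104.84, and 350/104.84 = 3.34. Power is 91.6% (normal) or 90.3% (t, 40 df).
- Inflation: 28/0.7 = 40 and 14/0.7 = 20.

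All the stated figures hold. The 80% is a two-sided, ungated figure with every randomized patient contributing.

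**Step 2: add the gate, with both SDs as stated.** From the rounded powers, independence gives 0.90 × 0.80 = 72%. Using the t-based powers and a bivariate normal for the two statistics:

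| PVR informative in | PVR power | Both pass, corr. 0 | corr. 0.5 | corr. 0.8 |
|---|---|---|---|---|
| 28/14 | 90.3% | 71.2% | 74.4% | 77.1% |
| 40/20 | 97.5% | 76.9% | 78.0% | 78.8% |

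Without any covariate adjustment, the gate costs about 2 to 8 points against 78.9% when PVR rests on 28/14, and at most 2 when it rests on all 60. Multiple imputation of PVR falls somewhere between, since it does not restore full information.

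**Step 3: allow for baseline adjustment.** If a covariate has correlation r with the change, the residual SD is SD × √(1 − r²). SAP 7.1 identifies 320.3 as the SD for change from baseline, so it precedes adjustment, and SAP 4.3.1 then adjusts for baseline PVR. Holding 6MWD at SD 65 m and PVR at 28/14:

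| Assumed r for PVR | PVR SD | PVR power | Both pass (corr. 0 to 0.8) |
|---|---|---|---|
| 0 | 320.3 | 90.3% | 71–77% |
| 0.3 | 305.5 | 92.7% | 73–78% |
| 0.5 | 277.4 | 96.4% | 76–79% |

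If 65 m also precedes adjustment, 6MWD gains too. Suppose the adjusted 6MWD SD is 60 to 62 m and the PVR SD shrinks in the same proportion. PVR becomes 320.3 × 62/65 = 305.5 or 320.3 × 60/65 = 295.7, ungated 6MWD power is 82.5% to 84.9%, and power to pass both is about 76.5% to 84% with PVR on 28/14.

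Plausible inputs therefore put the gated figure on either side of 80%, and the documents do not say which apply.

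**Step 4: the missing-data margin.** The 30% allowance concerns loss before the repeat catheterization. Walks are scheduled at Weeks 5, 10, 14, 18 and 22 and at early termination. A patient is lost to the 6MWD analysis only by leaving before Week 5 with no termination walk and no 0 m assignment. The documents give no rate for this, so applying 28/14 to 6MWD (63% by t) would overstate the loss.

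**The case for a change.** The strongest case for a change is that a reader of SAP 7.1 alone cannot tell what the 80% covers. On the inputs printed there, with no adjustment, the power to pass both tests is below 80% at every correlation. The paragraph is also uneven: PVR gets a dropout allowance and a sourced SD, and 6MWD gets neither. A few words would settle it.

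Much of this stands as description. The figure is not labelled as marginal, and the source and type of the 65 m SD are not given. The missing-data point has a sharper form as well: values carried forward from early visits may dilute the effect, and 0 m values widen the spread. If the effect in the imputed data were 45 m instead of 50 m (an assumed 10% dilution), power would be 70% at SD 65 m.

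What does not stand is the step to a shortfall. The below-80% result ignores the baseline adjustment that the plan applies to both endpoints. The dilution figure rests on an assumed rate, as would any loss rate for 6MWD. Replacing one correct sentence with ranges built on assumed correlations, SDs and loss rates would not make the plan more exact.

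**Conclusion.** No change follows. The 80% is correct for what it describes: one two-sided 5% test, 40/20 all contributing, 50 m, SD 65 m. Quoting marginal power for the second test in a fixed sequence is ordinary practice, and the gate is set out in SAP 4.3.1, Protocol 9.5.2.1 and both synopses. Anyone who needs the joint figure can derive it from the stated inputs.

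Without covariate adjustment that joint figure is about 71–77% with PVR on 28/14, assuming a correlation of 0 to 0.8 between the statistics. Adjusting PVR, 6MWD or both raises it, to about 76.5–84% under the equal-shrinkage assumption above. The documents support neither a claim that formal power is below 80% nor one that it is above.

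The unlabelled figure and the undefined SD are missing detail in a planning paragraph. Filling them in would leave the sample size, ANCOVA, imputation rules, testing order and success rule as they are. The study is declared positive on PVR alone, and the analysis will estimate the 6MWD residual variance from its own data whatever the 65 m represented.

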7.2 Method of Assigning Study Participants to Treatment Groups

Patients who meet all the entry criteria and are eligible for the study will report to the investigator to be randomized on Day 1. At the beginning of the dose titration period, eligible patients will be randomly assigned to receive 1 of 2 study treatments, either APD811 or placebo in a 2:1 ratio. Sites will randomize approximately 60 patients for entry into the study using an Interactive Web Randomization System (IWRS) across the entire study, and is not constrained within a center. Randomization will be stratified by Baseline WHO/NYHA Functional Class (Class II vs. III or IV).

7.3 Blinding/Unblinding

The sponsor, patients, and personnel involved with the conduct of the study will be blinded to the identity of study medication, with the exception of the independent statistician responsible for generating the randomization code and interacting with the SMC, and a representative from the bioanalytical lab conducting the pharmacokinetic (PK) analysis. All other personnel directly related to this study (i.e., investigators, site personnel, monitors, CRO personnel, Arena personnel) will remain blinded until patient completion of the study and the patient's data in the clinical database is locked, at which time the randomization code will be broken for the individual patient. The CRO will obtain written consent from Arena prior to breaking the code.

Breaking of the randomization code without Arena permission is expressly forbidden except in the event of a medical emergency where the identity of the study medication must be known in order to properly treat the patient. In the event of a medical emergency, it is requested that the Investigator make every effort to contact the study monitor or designee prior to breaking the code. If the blind is broken, the individual responsible should document the date, time, and reason for breaking the blind. A written report should be sent to Arena within one working day.

7.4 Handling of Missing Data and Sensitivity Analysis

For the ITT analysis of PVR missing week 22 assessments will be derived using the method of multiple imputation via the SAS/STAT procedure PROC MI and the fully conditional

specification (FCS) method to create 100 imputations resulting in 100 complete datasets. The 100 imputed datasets will then be analyzed using the methods described in Section 4.3.1, with the results of the analyses performed on the 100 datasets combined via PROC MIANALYZE. The imputation model will include the following variables: treatment, baseline PVR, baseline NYHA/WHO functional class category, baseline PAH therapy, baseline values for 6MWD, BNP, NT-proBNP, etiology, last on-treatment 6MWD and whether or not a patient experienced clinical worsening. It is anticipated that the imputation model will converge but should it not do so terms will be removed from the model to achieve convergence. The effects of any such model adjustment will be investigated.

To assess the impact of missing data and robustness of the results, the following sensitivity analyses will be performed for the primary, secondary and selected exploratory endpoints:

- Completers population analyses on primary and secondary efficacy endpoints will be performed without missing data imputation.
- Worst case imputation. For PVR, in all-treated patients, prior to ANCOVA analyses as detailed in Section 4.3.1 missing data at Week 22 due to any reason will be imputed by taking:
 - the worst percentage change from baseline in all patients regardless of treatment group.
 - the baseline observation carried forward.
- An additional 'tipping point analysis' *may* be performed for PVR, post-hoc, in the event that the primary analysis is statistically significant and at least 1 of the worst case imputation analyses yields a non-significant result.

For the proportion of patients who progress to clinical worsening, a sensitivity analysis to assess the impact of missing data will be performed wherein all patients who prematurely discontinue treatment for any reason will be considered to have had a clinical worsening event.

- Imputation of missing or incomplete AE start date
 - If year part of AE start date is missing, then the year of the first treatment date will be assigned.
 - If both month and day part of AE start date are missing, and the year part is the same as year of the first treatment date, then the first treatment date will be assigned;
 - If both month and day part of AE start date are missing, and year part is less than the year part of the first treatment date, then 'Dec31' will be assigned to the missing month and day part

- If both month and day part of AE start date are missing, and year part is greater than year part of the first treatment date, then 'Jan01' will be assigned to the missing month and day.
- If month part is present and day part is missing, and year and month are same as year and month of the first treatment date, then the first treatment date will be assigned;
- If month part is present and day part is missing, and year and month combination is before the year and month combination of the first treatment date, then the last day will be assigned;
- If month part is present and day part is missing, the year and month combination is after the year, month combination of the first treatment date, then '01' will be assigned to the missing day.

After imputing: if the date of AE end a complete date, and the imputed ASTDT is later than the date of AE end, then reassign AE start date as AE end date.

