Patients who meet the criteria for clinical worsening should be discontinued from study drug, and should undergo procedures for early termination. Patients who meet the criteria for clinical worsening do not qualify for entry into the extension study APD811-007 with the exception of placebo-treated patients.

Placebo-treated patients who discontinue study drug treatment due to clinical worsening in APD811-003 will be permitted to enroll in APD811-007, upon approval of the medical monitor, provided that all end of study procedures including right heart catheterization are performed per protocol.

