# 6.15 Removal of Patients from the Trial or Study Drug

The study will be terminated early if, in the opinion of the sponsor, investigator, or IRB/IEC, an unacceptable risk to the safety and welfare of patients is posed by the continuation of the study in light of review of the key safety data.

Patients will be informed that they are free to withdraw from the study at any time for any reason should they so wish. The PI may remove a patient if, in his/her opinion, it is in the best interest of the patient. A patient may be withdrawn from the study for any of the following reasons:

- Clinical worsening as defined in Section 6.9
- Deviation/noncompliance with the protocol,
- A serious or intolerable AE occurs,
- The sponsor or investigator terminates the study, or
- Withdrawal of consent any patient may withdraw his/her consent from the study at any time. The investigator should make a reasonable attempt to document the specific reason why consent is withdrawn.

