3 PATIENT DISPOSITION

The number of patients enrolled in the study by investigator and treatment group will be tabulated. Tables showing study participant accounting will be provided. Tables will indicate number of patients who were randomized into the study, the number of patients who completed the study, and the number of patients who discontinued prematurely (early termination) for any of the following reasons:

- Clinical worsening
- Deviation/noncompliance with the protocol or study drug
- Adverse event(s)
- Investigator decision
- Sponsor decision
- Patient withdrawal of consent
- Patient lost to follow up
- Death
- Other

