4.3.2 Secondary Efficacy Analyses

The percent change from baseline in PVR will be analyzed using the method described for change from baseline in PVR.

In addition, the PVR data (absolute value instead of change from baseline) will be natural log-transformed (\ln) prior to analysis. The dependent variable of the model is the change from baseline for the log-transformed endpoint value (i.e., $\ln(\text{Week 22 value}) - \ln(\text{baseline value})$) or equivalently the log-transformed ratio change from baseline (i.e., $\ln\left(\frac{\text{Week 22 value}}{\text{baseline value}}\right)$). Resultant LS mean estimates will be exponentiated to yield the geometric mean estimates of ratio changes from baseline; resultant LS mean difference estimates from placebo will be exponentiated to derive the geometric mean ratio estimates of ratio changes from baseline that is relative to placebo.

For the proportion of patients who progress to clinical worsening, number (%) of patients progressed in each treatment group and 95% CI will be reported; difference in proportion with 95% CI between treatment groups will be estimated using the method of Miettinen and Nurminen. The effect of APD811 will be compared to placebo using a logistic regression model with model with terms for treatment and baseline WHO/NYHA functional class (II vs. III or IV), and odds ratio and 95% CI will be reported.

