Appendix 3 Listing of Efficacy Parameters and Study Populations Analyzed

Efficacy Parameters	Response Analyzed	Study Populations Analyzed
Primary Endpoints		
PVR	Change from Baseline	ITT, CP
6MWD	Change from Baseline	MITT, CP
Secondary Endpoints		
Clinical Worsening	Proportion	MITT, CP
PVR	Percent Change from Baseline	ITT, , CP
Exploratory Endpoints		
BNP/NT-proBNP	Change from Baseline at Week 22	MITT, CP
WHO/NYHA functional class	Change in numeric scale from Baseline at Week 22	MITT, CP
WHO/NYHA functional class	Proportion of patients in categorical change of WHO/NYHA function class after 22 weeks of treatment.	MITT, CP
Hemodynamic parameters	Change from Baseline at Week 22	MITT
Longitudinal change from baseline in 6 MWD up to 22 weeks		MITT
Longitudinal change from baseline in WHO/NYHA functional class in numeric scale up to 22 weeks		MITT
Time to first event of clinical worsening		MITT

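### Clinical worsening is also analysed in completers, a population largely selected on not having worsened. As a minor point, the logistic odds ratio has no named CI type or test.

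*SAP*

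**What the plan says.** **The completers analysis.** SAP Section 7.4, under sensitivity analyses, states: "Completers population analyses on primary and secondary efficacy endpoints will be performed without missing data imputation". Section 4.1 makes the proportion with clinical worsening a secondary endpoint. The table in Appendix 3, "Listing of Efficacy Parameters and Study Populations Analyzed", gives both MITT and CP for it. Section 4.2 defines completers: "This population consists of all patients who completed the study treatment at Week 22". The same section asks that substantial differences between the conclusions from the populations be investigated.

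**What happens to a patient who worsens.** Protocol Section 6.9: "Patients who meet the criteria for clinical worsening should be discontinued from study drug, and should undergo procedures for early termination". The SAP takes the same view. Section 3 tabulates "the number of patients who discontinued prematurely (early termination) for any of the following reasons", and clinical worsening heads that list. The walk-distance rule in Section 4.3.1 imputes zero "if any patient withdraws early due to death or due to clinical worsening without a 6MWT being measured" at a termination visit. Protocol Section 6.15 is more permissive: "A patient may be withdrawn from the study for any of the following reasons", with clinical worsening among the reasons.

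**The model.** SAP Section 4.3.2: "The effect of APD811 will be compared to placebo using a logistic regression model", with terms for treatment and baseline functional class. An odds ratio with 95% CI is to be reported, together with a Miettinen-Nurminen CI for the difference in proportions. The type of CI for the odds ratio, the test behind the comparison, and the handling of an arm without events are not given.

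**Safeguards already in the plan.** MITT is the main population for this endpoint. Section 7.4 also plans a sensitivity analysis that counts every premature discontinuation of treatment as a worsening event. Section 6.3 classes comparisons other than PVR and 6MWD as supportive or exploratory.

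**The concern.** A completers analysis of PVR or walk distance asks what the result looks like among patients with observed Week 22 data. For clinical worsening the question does not carry over. The event is itself a reason for leaving treatment, so restricting to completers removes most patients who had it. What remains is a comparison of two groups that have mostly not worsened, and it will look similar between arms even if the drug prevents worsening or causes it. Because Section 4.2 asks for differences between populations to be investigated, the plan would set off an inquiry into a discrepancy that it had built in.

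The second, smaller concern is that worsening events may be few with 40 and 20 patients. If one arm has none, the maximum-likelihood odds ratio is zero or infinite and a Wald CI is unusable. Other tests from the same model still give an answer, but not always on the same side of 0.05. The plan does not say which is to be reported.

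**Working it through.** **Inputs from the documents.** Arm sizes are 40 and 20 (SAP Section 7.1). They follow from the plan's own sizing: 28/(1 − 0.30) = 40 and 14/(1 − 0.30) = 20. No event rate, power or sample size is given for clinical worsening, so every event count or rate below is an assumption.

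**Step 1: the completers comparison.** Assume 2/40 worsen on APD811 and 4/20 on placebo. The MITT difference is 5.0% − 20.0% = −15.0 points. Let r be the share of worsened patients who still count as completers, the same in both arms and independent between patients. Assume also that every patient who does not worsen completes.

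- Expected events: 2r and 4r. Expected completers: 40 − 2(1 − r) and 20 − 4(1 − r).
- Difference = 2r/(40 − 2(1 − r)) − 4r/(20 − 4(1 − r)).
- Chance that at least one arm is empty = 1 − [1 − (1 − r)²][1 − (1 − r)⁴].

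| r | APD811 | Placebo | Difference (points) | Empty arm |
|---|---|---|---|---|
| 0 | 0/38 | 0/16 | 0 | 100% |
| 10% | 0.2/38.2 | 0.4/16.4 | −1.9 | 93% |
| 25% | 0.5/38.5 | 1/17 | −4.6 | 70% |
| 50% | 1/39 | 2/18 | −8.5 | 30% |

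**Step 2: how much the choice of test matters when an arm is empty.** The logistic model has treatment and functional class, with an assumed 50:50 class split (cells of 20, 20, 10 and 10).

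- 0/40 vs 2/20, one placebo event per class: likelihood-ratio p = 0.033; Firth-penalised p = 0.073 (odds ratio 0.10, CI 0.0007 to 1.22); Fisher p = 0.107. The Miettinen-Nurminen interval is −30.3 to −0.5 points.
- 0/40 vs 3/20: 0.008, 0.022 and 0.033 in the same order. 0/40 vs 4/20: 0.002, 0.007 and 0.010. The conclusions agree.
- In the Wald case, shown for a treatment-only model at 0/40 vs 3/20, the p-value drifts with the iteration count: 0.44 after 8 iterations and 0.997 after 21.

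**Step 3: how often this would occur.** All possible tables were enumerated exactly under assumed rates. The third column is the chance that the likelihood-ratio and Firth tests fall on opposite sides of 0.05 in a table with an empty arm. The last two columns are rejection rates, which are type I error where the two arms have equal rates.

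| Placebo / APD811 rate | Empty arm | Tests disagree | Likelihood ratio | Firth |
|---|---|---|---|---|
| 5% / 5% | 44% | 4.0% | 5.6% | 1.6% |
| 10% / 10% | 13.5% | 3.7% | 7.4% | 3.5% |
| 20% / 20% | 1.2% | 0.2% | 6.0% | 4.7% |
| 20% / 10% | 2.6% | 0.5% | 18.7% | 18.0% |
| 20% / 5% | 13.9% | 1.8% | 43.1% | 41.2% |
| 15% / 2.5% | 39% | 8.3% | 46.7% | 38.4% |

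**The case against.** **On the completers analysis,** the case for leaving it alone is that nothing depends on it. MITT is the main population, the other sensitivity analysis works in the opposite direction, and anyone investigating a discrepancy would see the selection at once. That is fair and limits the consequence. It does not give the analysis a purpose: it cannot inform on robustness to missing data, because it deletes the events themselves.

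A reader might infer that the completers analysis can contain no events at all. The documents do not support that. Section 6.9 says such patients should be discontinued, but Section 6.15 says only that they may be withdrawn, and an event at or after the Week 22 visit can fall in a completer. Hence largely, not wholly, selected.

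**On the odds ratio,** three stronger readings are tempting and should be resisted.

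- That no confidence interval is planned. Section 4.3.2 does plan a 95% CI; only its type is unnamed.
- That an arm without events leaves the endpoint unanalysable. The Miettinen-Nurminen difference still works, and so does a likelihood-ratio test when there is at least one event.
- That the chance of an empty arm is the chance of a changed conclusion. It is far smaller: 4.0% against 44% when both rates are 5%. A Wald test would diverge more, but the plan does not name one.

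Nor does the plan provide for choosing the test after seeing the data. It is silent, and silence leaves that possibility open.

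**Conclusion.** The completers point holds. Under the plan as written, a secondary endpoint is analysed in a population largely defined by its absence, and the comparison is pulled towards zero. In the illustration, 15 points become between 0 and 8.5. The size rests on assumed counts, on equal retention of worsened patients in both arms, and on all other patients completing. The plan itself allows up to 30% dropout before the repeat catheterisation, so real denominators would be smaller. The mechanism does not depend on the particular counts.

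The unnamed CI type and test are a real but minor omission. Under the rates tabulated, the likelihood-ratio and Firth tests disagree at 0.05 because of an empty arm with a probability of 0.2% to 8.3%.

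Neither part threatens the trial's main conclusion. The endpoint is secondary, unpowered and supportive, and the study is declared positive on PVR alone.

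**What to change.** **Completers.** Remove CP from the clinical worsening row of SAP Appendix 3, and exempt this endpoint from the completers analysis in Section 7.4. Keep the MITT analysis and the planned sensitivity analysis that treats all premature discontinuations as events. This costs one table cell and one clause, needs no data, and loses no useful information.

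**Odds ratio.** In Section 4.3.2, name one method for all cases: Firth-penalised logistic regression with the planned terms, a profile penalised-likelihood CI and a penalised likelihood-ratio p-value, reported beside the Miettinen-Nurminen difference. If neither arm has events, report only the proportions and their difference.

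The price is conservatism when events are rare, with type I error of about 1.6% and 3.5% at common rates of 5% and 10%. Compared with a likelihood-ratio test throughout, the loss of power in the scenarios above runs from 18.7 − 18.0 = 0.7 points to 46.7 − 38.4 = 8.3 points. The likelihood-ratio test, however, exceeds 5% type I error at each common rate tabulated. Using Firth only when an arm is empty gains almost nothing (power 41.2% either way at 20% vs 5%) and makes the method depend on the data, so a single method is preferable.
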